Ab=antibody; ADE=adverse device effect; AE=adverse event; BKZ=bimekizumab; BSA=body surface area; CT=computed axial tomography; DLQI=Dermatology Life Quality Index; ECG=electrocardiogram; eCRF=electronic Case Report Form; HBcAb=anti-hepatitis B core antibody; HBsAg=hepatitis B surface antigen; HBV=hepatitis B virus; HCV=hepatitis C virus; HIV=human immunodeficiency virus; IGA=Investigator's Global Assessment; IGRA=interferon-gamma release assay; IMP=investigational medicinal product; IRT=interactive response technology; P-SIM=Psoriasis Symptom and Impact Measure; PASI=Psoriasis Area and Severity Index; PEOT=Premature End of Treatment; PSD=Patient Symptom Diary; Q4W=every 4 weeks; Q8W=every 8 weeks; scalp IGA=scalp-specific IGA; SFU=Safety Follow-Up; TB=tuberculosis

Note: All assessments should be performed prior to IMP administration. The IMP administration is the starting point for the next administration period. Thus, the assessments in Week 16 and Week 32 belong to the previous treatment period.

^a For visits from the first dose of IMP through Week 32, the visit window is ± 4 days from the scheduled visit. For the SFU Visit, the visit window is ± 7 days from the scheduled visit.

^b The SFU Visit will occur 17 weeks after the final dose of IMP.

^c Ensure no significant changes in medical history.

^d Includes evaluation of signs and symptoms of active TB and risk for exposure to TB.

^e The physical examination will be performed as described in Section 8.2.3.

^f Vital signs (sitting systolic and diastolic blood pressure, pulse rate, and body temperature) are to be measured prior to blood sampling and prior to dosing, where applicable.

^g Pregnancy testing will consist of serum testing at Screening. A urine pregnancy test will be administered at all other visits.

^h Study participants who have evidence of or test positive for hepatitis B or C are excluded from the study, per Exclusion Criterion #9 (Section 5.2). A positive test for HBV is defined as: 1) positive for HBsAg or 2) positive for HBcAb. A positive test for HCV is defined as: 1) positive for anti-HCV Ab and 2) positive via a confirmatory test for HCV (eg, HCV polymerase chain reaction).

ⁱ The HIV test results will not be recorded in the eCRF.

^j Screening chest x-ray/CT scan must occur within 3 months prior to Screening Visit.

Table 1-1: Schedule of Activities

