9.4.1.2 Hematology/biochemistry

Treatment-emergent markedly abnormal (TEMA) laboratory values are those that have an assessment date on or following first dose of IMP.

Laboratory assessments will be analyzed by visit. Absolute values and changes from Baseline in each laboratory parameter will be presented descriptively for each treatment group. The incidence rate of TEMA laboratory values at the parameter level will also be presented descriptively for each treatment group. Definitions for markedly abnormal laboratory values will be provided in the SAP.

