- For study participants who discontinue the ITP early or who complete the ITP but do not continue to the MTP, use the minimum of the following:

Date of last dose in the ITP – Date of first dose in the ITP + 119

Date of last clinical contact – date of first dose in the ITP + 1

For study participants who are randomized to placebo in ITP and switch to BKZ 320mg Q4W in MTP:

Include time at risk in MTP defined in section 4.5.1.2 – time at risk.

- For BKZ 320mg Q8W:

Include time at risk in MTP for study participants who switch to BKZ 320mg Q8W in MTP (refer to section 4.5.1.2 – time at risk).

- For BKZ 320mg Total:

For study participants randomized to BKZ 320mg Q4W in ITP:

- For study participants who died before the final visit (not including SFU):

Date of death – date of first dose in the ITP + 1

- For all the other study participants including who discontinue early or who complete the MTP as scheduled, use the minimum of the following:

Date of last dose – Date of first dose in the ITP + 119

Date of last clinical contact – date of first dose in the ITP + 1

For study participants who are randomized to Placebo in ITP and switch to BKZ 320mg Q4W in MTP:

Include time at risk in MTP defined in section 4.5.1.2 – time at risk

A by-study participant listing of exposure to study medications will be provided on the SS by treatment group.

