4.5.2.1 Data considerations

TEAEs are defined as those AEs that have a start date on or following the first dose of IMP through the final dose of IMP + 119 days (covering the 17-week SFU period). If it is not possible (due to partial dates) to determine whether or not an AE is treatment-emergent then it will be assumed to be a TEAE.

The rules for imputing partial AE start or stop dates are described in Section 6.8.1.2.

If the intensity of an AE is unknown, it is considered as severe. If the relationship to study drug is missing, it is considered as related.

AEs will be presented as “number of study participants (percentage of study participants) [number of events]”. In this style of output, “[number of events]” will include all cases of an AE including repeat occurrences in individual study participants, while “number of study participants” will count each study participant only once.

AE summaries by System Organ Class (SOC), High Level Term (HLT) and Preferred Term (PT) will be ordered alphabetically for SOC and HLT within SOC and in terms of decreasing frequency for PT within HLT in the bimekizumab treatment group, and in the event of ties, PT will be sorted alphabetically.

AE summaries by PT will be ordered in terms of decreasing frequency for PT within the bimekizumab treatment group, and in the event of ties, PT will be sorted alphabetically.

Study participant time at risk represents the time a study participant is at risk for having an AE. The definitions for study participant time at risk (in days) are outlined in Section 4.5.1. These definitions will be used for exposure-adjusted AE summaries.

Selected AE summaries will include the exposure-adjusted incidence rate (EAIR) with associated 95% CI and the exposure-adjusted event rate (EAER).

The EAIR is defined as the number of study participants (n) with a specific AE adjusted for the exposure and will be scaled to 100 patient-years:

$$EAIR = 100 \times n / \sum_{i=1}^N (T_{Exp(i)})$$

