4.5.3 Additional safety assessments

4.5.3.1 Clinical laboratory evaluations

Laboratory values, including markedly abnormal laboratory values will be presented descriptively by treatment group for the SS.

Tables presenting markedly abnormal values and those based on CTCAE grade (see section 6.13) will only include selected laboratory variables.

For tables where data are summarized by visit, unscheduled and repeat visits will not be summarized, but these data will be included in listings. Assessments collected at SFU visit should be included in by-visit tables. For tables where multiple measurements over a period of time are considered (as in shift tables), unscheduled and repeat visits will be considered as long

as they were collected in the period being summarized. All summaries will be presented in SI units and will be based on observed case values. In the case where laboratory values are below the lower limit of quantification, then these will be set to the midpoint between 0 and the lower limit of quantification for the purpose of summarizing the data. Only central laboratory results will be used in table analysis, while local laboratory results will only be displayed in listings.

For summaries for the ITP and Initial and Maintenance Period (combined) where multiple measurements across different visits are considered (as of markedly abnormal values tables, minimum/maximum post-baseline CTCAE tables, and shift tables), the laboratory results will be attributed according to their sampling date and time at risk for each period (see Section 4.5.1).

The following analyses will be presented:

- A summary of the absolute and change from Baseline values in each laboratory variable by treatment group and visit for the SS displaying the Placebo/BKZ 320mg Q4W and BKZ 320mg Q4W/Q8W.
- A summary of the number and percentage of study participants experiencing markedly abnormal values at any time while on treatment (ie, assessment on or following the first dose of IMP through the last dose of IMP + 119 days, occurring at scheduled and unscheduled visits) by laboratory variable and treatment group. Baseline values and values observed more than 119 days after the last administration of IMP are not considered. Two separate tables will show results for the ITP (for the SS) and the initial and maintenance treatment period (combined) (for the AMS). See section 6.10.1 for the criteria for markedly abnormal values.

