6.10.2 Criteria for Markedly abnormality for vital signs data

The definitions of markedly abnormal vital sign values are provided below:

Table 6-8: Definitions of Markedly Abnormal Blood Pressure Values

| Parameter (unit) | Markedly Abnormal Low | Markedly Abnormal High |
|---------------------------------|---|---|
| Systolic blood pressure (mmHg) | <90 and a decrease from Baseline of ≥20 | >180 and an increase from Baseline of ≥20 |
| Diastolic blood pressure (mmHg) | <50 and a decrease from Baseline of ≥15 | >105 and an increase from Baseline of ≥15 |

For this summary, Baseline values and values observed more than 119 days after the last administration of study medication are not considered.

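### The SAP's 119-day limit falls on the scheduled SFU day and ignores the +7 side of the visit window, so on-protocol SFU values on days 120 to 126 are left out of the combined-period abnormality tables

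*SAP*

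**What the plan says.** **Visit.** The footnotes to the Schedule of Activities (Protocol 1.3) state "The SFU Visit will occur 17 weeks after the final dose of IMP" and "For the SFU Visit, the visit window is ± 7 days from the scheduled visit". SAP 4.1 repeats the window. The schedule marks hematology, biochemistry and vital signs at SFU, and this is the only planned measurement of them after Week 32.

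**Explicit limits.**
- Markedly abnormal laboratory table (SAP 4.5.3.1): "Baseline values and values observed more than 119 days after the last administration of IMP are not considered".
- Markedly abnormal blood pressure table (SAP 6.10.2): "values observed more than 119 days after the last administration of study medication are not considered".
- TEAEs (SAP 4.5.2.1) run from the first dose "through the final dose of IMP + 119 days (covering the 17-week SFU period").

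**Indirect limit.** For the markedly abnormal, CTCAE minimum/maximum and shift tables, SAP 4.5.3.1 says that results are "attributed according to their sampling date and time at risk for each period". SAP 4.5.3.2 has a parallel rule for vital signs. In the combined period, time at risk for the BKZ Total column is the smaller of the time to last clinical contact and "Date of last dose – Date of first dose in the ITP + 119" (SAP 4.5.1.3). SAP 4.5.1.2 caps the MTP in the same way.

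**Protocol definition.** Protocol 9.4.1.2 sets no end date: "Treatment-emergent markedly abnormal (TEMA) laboratory values are those that have an assessment date on or following first dose of IMP". Protocol 9.4.1.1 sets none for TEAEs either. SAP 4.8 declares one departure from the protocol, on key secondary sensitivity analyses, and does not mention a 119-day limit.

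**The concern.** The limit equals the nominal SFU day, but the visit may take place up to a week later and still be on protocol. SAP 4.1.1.2 ends the SFU Period on the day the visit takes place, so for a visit on days 120 to 126 a limit of +119 days does not reach the end of that period.

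Whether a Grade 3 laboratory value at SFU enters the markedly abnormal table then depends on a permitted scheduling difference of one day. The exclusion can only lower the number of participants counted. It also makes the report disagree with itself. ALT above 5 times ULN is a markedly abnormal value in SAP 6.10.1, and it is also a row of the liver-function elevation table in SAP 4.5.3.1, which covers the whole study. An ALT result at that level on day 122 would appear in the second table and not in the first.

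At stake is the completeness of the pooled descriptive summaries that serve the tertiary objective of safety over the whole study. No efficacy result or hypothesis test is involved.

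**Working it through.** **Inputs.** SFU timing and window: Protocol 1.3. Cut-offs: SAP 4.5.2.1, 4.5.3.1 and 6.10.2. Time at risk: SAP 4.5.1.1 to 4.5.1.3. Planned randomization: about 120 (90 + 30), SAP 1.2. The spread of actual SFU days is not given in either document and is an assumption throughout.

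**1. The plan's figure.** 17 weeks × 7 = 119 days, which reproduces the SAP limit exactly.

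**2. Window against limit.** On-protocol days run from 119 − 7 = 112 to 119 + 7 = 126, which is 15 days. Days 120 to 126 lie beyond the limit, which is 7 days. 7/15 = 46.7% of the allowed days.

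**3. From days to visits.** The excluded share of visits depends on when participants attend. The counts assume that all 120 attend SFU and belong to the AMS, so they are upper values.

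| Assumed SFU timing within the window | Share after day 119 | Of 120 |
|---|---|---|
| Uniform: 7/15 | 46.7% | 56 |
| Triangular around day 119: 28/64 | 43.8% | 52 |
| Normal around day 119, SD 2 to 3 days | 40.0% to 43.3% | 48 to 52 |
| Half exactly on day 119, rest even: 0.5 × 7/14 | 25.0% | 30 |
| Normal around day 117, SD 2 to 3 days | 10.4% to 20.7% | 12 to 25 |
| Normal around day 121, SD 2 to 3 days | 68.2% to 77.5% | 82 to 93 |

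**4. Which tables are affected.**
- *Combined-period markedly abnormal laboratory and blood pressure tables (AMS):* excluded by explicit text. SAP 6.10.2 defines markedly abnormal vital signs only for systolic and diastolic pressure.
- *Combined-period CTCAE minimum/maximum and shift tables:* no explicit cut is stated. The exclusion is inferred from attribution by time at risk.
- *ITP tables:* not affected. Under SAP 4.5.1.1, time at risk ends at the first MTP dose for those who continue. For those who stop early or do not continue, it is at most 112 days from the first dose.
- *By-visit laboratory tables:* SFU results are kept (SAP 4.5.3.1).
- *Liver-function elevation table, Grade 3/4 listing, full laboratory and vital-sign listings, AE listings:* no 119-day limit is stated.

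**5. AE rates.** TEAEs stop at last dose + 119 days, and time at risk is capped at about the same point. Numerator and denominator of the EAIR and EAER are truncated together, so the cut does not by itself bias the rates. AEs starting on days 120 to 126 are not TEAEs, although Protocol 8.3.1 collects AEs until the SFU Visit.

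**6. With the limit at the in-window SFU date.** The latest compliant visit is at +126 days, so 0 of the 15 allowed days are excluded.

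**The case against.** The 17-week horizon is deliberate. The protocol uses it for SAE collection (8.3.1), for following abnormal laboratory values (8.2.1) and for the SFU Period itself. The SAP counts placebo injections in the MTP as IMP (4.1), and the Q8W arm receives placebo at Week 28. For about 90 of 120 participants, last IMP + 119 days is therefore already 28 + 119 = 147 days after the last active dose at Week 24. The SAP version history shows that the exposure rules were aligned with the global studies. The affected combined-period tables are descriptive and have no placebo column. A participant is lost from a count only if the sole markedly abnormal value fell on days 120 to 126.

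All of this stands as a limit on the importance of the point. It does not explain why a compliant visit should count on day 119 and not on day 120.

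A reader might infer three stronger claims, which the documents do not support:

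- *That the SAP stops counting safety data at day 119, or loses these values.* It does not. They remain in the by-visit laboratory tables, the liver-function elevation table and the listings, including a listing of every Grade 3 or 4 laboratory result.
- *That nearly half of SFU results are dropped.* 7/15 is a share of window days. It becomes a share of results only under an assumed attendance pattern.
- *That a visit exactly on day 119 is lost as well, giving 8/15 = 53%.* Counted inclusively from the first-dose day, a duration of last − first + 119 days does end at last dose + 118. But SAP 4.5.3.1 expressly runs the markedly abnormal window up to 119 days after the last dose. Reading a duration formula as a date cut that overrides that text is inference. The one-day mismatch is worth tidying and no more.

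**Conclusion.** The point holds in a limited form. The limit ignores the later half of the SFU window, so on-protocol laboratory, systolic and diastolic values on days 120 to 126 (7 of 15 allowed days) are excluded from the combined-period markedly abnormal tables. They are apparently also excluded from the CTCAE minimum/maximum and shift tables, where the conclusion rests on how the attribution rule is read.

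The excluded share of visits is about 47% under uniform attendance and roughly 10% to 78% across the patterns tried. The effect on the abnormality counts themselves is downward or nil. It cannot be sized from the documents, because it depends on how many participants have their only qualifying value in those seven days.

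The SAP limit is also narrower than the protocol's definitions of TEAEs and TEMA values, and SAP 4.8 does not say so. The protocol leaves further detail of the TEAE summaries to the SAP, but an end date changes the definition and should be declared. Safety through Week 16, all placebo comparisons and the exposure-adjusted AE rates are unaffected.

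**What to change.** In SAP 4.5.3.1, 4.5.3.2 and 6.10.2, end the window for the combined-period markedly abnormal, CTCAE and shift tables at the later of (a) last IMP dose + 119 days and (b) the date of an in-window SFU Visit, so at most last dose + 126 days. State that this rule overrides the time-at-risk cap for those tables. Otherwise the attribution rule would reimpose the cut.

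For TEAEs and time at risk, choose one of two options and write it down:
- apply the same limit to both, so that numerator and denominator still match; or
- keep +119 days for consistency with the program, and list it in SAP 4.8 as a change from Protocol 9.4.1.1.

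Moving every TEAE and exposure window to 126 days is not needed to repair the abnormality tables.

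The cost is a few lines of SAP text, one changed constant in the programs and a slight difference from the program convention. If TEAEs are extended too, time at risk grows by at most 7 days per participant.

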8.3.7 Other safety topics of interest

Prespecified safety topics of interest for this study are as follows: infections (serious, opportunistic, fungal, and TB), neutropenia, hypersensitivity, injection site reactions, neuropsychiatric AEs (including SIB), major CV events, LFT changes/enzyme elevations, malignancies, and IBD.

These safety topics of interest are based on findings from the bimekizumab clinical program to date, potential risks generally associated with biologic immunomodulators, or findings from other medicines with a related mechanism of action. There are no specific AE reporting requirements for these topics, however, special monitoring, additional data collection activities, and/or enhanced signal detection activities within UCB are in place.

The reporting requirements for events relating to TB are as follows:

- Interferon-gamma release assay test conversion, defined as a positive or indeterminate (and confirmed indeterminate on repeat) IGRA result for the current test when previous IGRA test results were negative, should be reported as an AE (Section 8.2.5.3.4). The AE term would need to be updated with final diagnosis once available.
- Latent TB infection must be reported as an AE (Section 8.2.5.3.5). Follow-up reports should be completed as described in Section 10.3 (Appendix 3) until the LTBI resolves.
- Confirmed active TB is always considered an SAE and must be captured on an SAE Report Form and provided to the Sponsor in accordance with SAE reporting requirements (Section 10.3 [Appendix 3]). Follow-up reports should be completed as described in Section 10.3 (Appendix 3) until the TB infection resolves (Section 8.2.5.3.6).

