4.1.4 Treatment assignment and treatment groups

It is expected that study participants receive treatment as randomized for the ITP, or as assigned per protocol study design (via reallocation) for the MTP.

Safety analyses will be based on the SS, as randomized. However, if after unblinding it is determined that study participants randomized to placebo received bimekizumab at any time within the first 16 weeks, then for safety analyses these study participants will be reallocated to the appropriate bimekizumab treatment group, unless otherwise specified. Study participants randomized to bimekizumab will only be reallocated to the placebo treatment group if they never received bimekizumab.

Unless otherwise stated, the summary tables of safety analyses will be provided as:

- The ITP data will be displayed by Placebo and BZK 320mg Q4W columns based on the SS
- The MTP data will be displayed by BKZ 320mg Q4W and BKZ 320mg Q8W columns based on the MS by treatment received at the MTP
- The initial and maintenance treatment period data will be displayed by BKZ 320mg Q4W, BKZ 320mg Q8W, and BKZ 320mg Total columns based on the AMS

Study participants randomized to BKZ 320mg Q4W and received BKZ 320mg Q8W in the MTP will be represented in both the BKZ 320mg Q4W and BKZ 320mg Q8W treatment columns. BKZ 320mg Q8W column only presents the data after the switch from BZK 320mg Q4W to BKZ 320mg Q8W. BKZ 320mg Q4W column will also include study participants that switch from Placebo to BKZ 320mg Q4W (only data after switch).

Efficacy analyses should be performed according to randomized treatment and not actual treatment received.

Unless otherwise stated, the summary tables of efficacy analyses will be provided as:

- The ITP data will be displayed by Placebo and BZK 320mg Q4W columns based on the RS
- The MTP data will be displayed by BKZ 320mg Q4W column and BKZ 320mg Q8W column based on the MS by treatment received at the MTP
- The initial and maintenance treatment period data will be displayed by Placebo/BKZ 320mg Q4W and BZK 320mg Q4W/Q8W columns based on the randomized treatment sequence by RS

For all TFLs for demographics, baseline disease characteristics, previous and ongoing medical history, prior and concomitant medications, and psoriasis treatment history, the summary will be displayed by Placebo/BKZ 320mg Q4W and BKZ 320mg Q4W/Q8W columns based on the randomized treatment sequence.

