- A summary of the number and percentage of study participants with a given CTCAE grade (0,1,2,3, or 4) based on minimum/maximum post-baseline value by laboratory variable and treatment group. Two separate tables will show results for the ITP (for the SS) and the initial and maintenance treatment period (combined) (for the AMS).
- Shift tables of the number and percentage of study participants experiencing CTCAE grade 0,1,2,3, or 4 values (as applicable) at Baseline to minimum/maximum post-Baseline CTCAE grade, by laboratory variable and treatment group. Two separate tables will show results for the ITP (for the SS) and the initial and maintenance treatment period (combined) (for the AMS).
- By-study participant listings of all laboratory data (including urinalysis) will be provided. These listings will be presented by treatment group and will include: center, study participant identifier, age, sex, race, weight, visit, laboratory variable, result (with abnormal values flagged as “L” or “H” accordingly) and unit.
- A separate listing will be provided for laboratory results classified as Grade 3 or Grade 4 for the SS.

The table for markedly abnormal liver function tests (LFTs) will contain data beyond the CTCAE Grade 3 thresholds outlined in Section 6.10.1 in order to allow for a more thorough review of elevated LFTs. There will be one table which will list the count and percentage of study participants meeting the below criteria at any time during the study:

- AST: >3xUpper Limit of Normal (ULN), >5xULN, >8xULN, >10xULN, >20xULN
- ALT: >3xULN, >5xULN, >8xULN, >10xULN, >20xULN

- AST or ALT: >3xULN, >5xULN, >8xULN, >10xULN, >20xULN
- Bilirubin: >1.5xULN, >2xULN
- ALP: >1.5xULN

For any participant with at least one markedly abnormal LFT (AST >3xULN, ALT >3xULN, bilirubin >3xULN, or ALP >1.5xULN) the New Ratio (nR) will be calculated as the ratio of either maximum ALT or maximum AST (whichever is higher) to ALP, all expressed as multiples of their ULN as follows:

- $nR = [\text{maximum}(\text{ALT/ULN or AST/ULN})]/(\text{ALP/ULN})$

A plot displaying shift in liver function tests from baseline to maximum post-baseline result and a plot showing maximum post-baseline Total Bilirubin versus maximum post-baseline AST and ALT will be provided for the AMS if there are study participants with reported markedly abnormal LFT.

The following definition of potential drug induced liver injuries (pDILI) will be used (all criteria must be met at the same assessment):

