6.10 Appendix 10: Potentially Clinically Significant Criteria for safety endpoints

6.10.1 Criteria for Markedly abnormality for laboratory data

Markedly abnormal values are defined as those with a severity of Grade 3 and above based on the CTCAE criteria (U.S. Department of Health and Human Services 2010). Definitions of markedly abnormal values using the Grade 3 cut points are given in the tables below for age ranges of ≥ 17 years (Table 6-5 for markedly abnormal liver function test values, Table 6-6 for markedly abnormal biochemistry values, and Table 6-7 for markedly abnormal hematology values).

Table 6-5: Definitions of Markedly Abnormal Liver Function Values

| Parameter name | Conventional | | Standard | | Abnormal designation |
|----------------------|--------------|--------------------------|----------|--------------------------|----------------------|
| | Unit | Criteria | Unit | Criteria | |
| Alkaline Phosphatase | | $>5.0 \times \text{ULN}$ | | $>5.0 \times \text{ULN}$ | AH |
| ALT | U/L | $>5.0 \times \text{ULN}$ | U/L | $>5.0 \times \text{ULN}$ | AH |
| AST | U/L | $>5.0 \times \text{ULN}$ | U/L | $>5.0 \times \text{ULN}$ | AH |
| Total Bilirubin | mg/dL | $>3.0 \times \text{ULN}$ | umol/L | $>3.0 \times \text{ULN}$ | AH |
| GGT | U/L | $>5.0 \times \text{ULN}$ | U/L | $>5.0 \times \text{ULN}$ | AH |

Table 6-6: Definitions of Markedly Abnormal Biochemistry Values

| Parameter name | Conventional | | Standard | | Abnormal designation |
|----------------|--------------|--------------------------|----------|--------------------------|----------------------|
| | Unit | Criteria | Unit | Criteria | |
| Creatinine | mg/dL | $>3.0 \times \text{ULN}$ | mmol/L | $>3.0 \times \text{ULN}$ | AH |
| Glucose | mg/dL | <40 | mmol/L | <1.7 | AL |
| | | >250 | | >13.9 | AH |
| Calcium | mg/dL | >12.5 | mmol/L | >3.1 | AH |
| | | <7.0 | | <1.75 | AL |
| Potassium | mmol/L | >6.0 | mmol/L | >6.0 | AH |
| | | <3.0 | | <3.0 | AL |

| Parameter name | Conventional | | Standard | | Abnormal designation |
|----------------|--------------|--------------|----------|--------------|----------------------|
| | Unit | Criteria | Unit | Criteria | |
| Sodium | mmol/L | >155 <130 | mmol/L | >155 <130 | AH AL |
| Cholesterol | mg/dL | >400 | mmol/L | >10.34 | AH |

Table 6-7: Definitions of Markedly Abnormal Hematology Values

| Parameter name | Conventional | | Standard | | Abnormal designation |

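### The graded liver-enzyme table is planned once for the whole study, so no ITP table counts liver test elevations below Grade 3 against placebo

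*SAP*

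**What the plan says.** Protocol 8.3.7 names liver tests among the prespecified safety topics: "LFT changes/enzyme elevations, malignancies, and IBD".

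SAP 4.5.3.1 introduces the liver table this way: "The table for markedly abnormal liver function tests (LFTs) will contain data beyond the CTCAE Grade 3 thresholds outlined in Section 6.10.1". It continues: "There will be one table which will list the count and percentage of study participants meeting the below criteria at any time", the period being the whole study. The cut-offs are AST, ALT, and either of them, at >3x, >5x, >8x, >10x and >20xULN; bilirubin at >1.5x and >2xULN; and ALP at >1.5xULN. The paragraph states no analysis set, treatment columns or restriction to post-Baseline values.

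The three any-time summaries listed before it in the same section (markedly abnormal values, worst CTCAE grade, and CTCAE shift) each carry this instruction: "Two separate tables will show results for the ITP (for the SS) and the initial and maintenance treatment period (combined) (for the AMS").

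SAP 6.10.1 sets the level for the general table: "Markedly abnormal values are defined as those with a severity of Grade 3 and above based on the CTCAE criteria". For liver tests, Table 6-5 puts this at >5xULN for ALT, AST, ALP and GGT, and >3xULN for total bilirubin. The graded CTCAE tables are limited in scope: "Tables presenting markedly abnormal values and those based on CTCAE grade (see section 6.13) will only include selected laboratory variables".

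SAP 4.1.4 gives default safety columns. ITP data are shown as Placebo and BKZ 320mg Q4W on the Safety Set (SS). For the combined period: "The initial and maintenance treatment period data will be displayed by BKZ 320mg Q4W, BKZ 320mg Q8W, and BKZ 320mg Total columns", on the Active Medication Set (AMS).

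**The concern.** Every placebo participant who continues receives bimekizumab from Week 16 (Protocol 4.1), so the first 16 weeks are the only randomised, placebo-controlled evidence on liver enzymes. A single whole-study table loses that comparison under either plausible layout. With the combined-period columns of SAP 4.1.4 there is no placebo column. With columns by randomised sequence, the control column mixes placebo time with bimekizumab time.

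The SAP itself treats the lower range as worth reporting. Its trigger for calculating the New Ratio in 4.5.3.1 counts AST or ALT >3xULN, or ALP >1.5xULN, as a markedly abnormal liver test, although 6.10.1 uses >5xULN. What is at stake is a simple count, by randomised arm, of participants in that range during the controlled period.

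**Working it through.** **1. Does another planned output fill the gap?**

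| Output | Period and set | Threshold count below Grade 3 against placebo? |
|---|---|---|
| Graded LFT table (SAP 4.5.3.1) | Whole study; set and columns not stated | No, as written |
| Markedly abnormal values (4.5.3.1, Table 6-5) | ITP on SS; combined on AMS | No: starts at ALT/AST/ALP >5xULN, bilirubin >3xULN |
| CTCAE worst grade and shift (4.5.3.1, Tables 6-9 and 6-10) | ITP on SS; combined on AMS | No: no ALT, AST, ALP, GGT or bilirubin rows |
| LFT plots (4.5.3.1) | AMS | No randomised placebo comparison |
| pDILI and potential Hy's Law (4.5.3.1) | Period not stated | Needs ALT/AST >=3xULN together with raised bilirubin |
| By-visit values and changes (4.5.3.1) | SS, by randomised sequence | Placebo-controlled up to Week 16, but descriptive values; unscheduled and repeat samples left out |
| Hepatic-event TEAEs (4.5.2.4, 4.5.2.4.8) | ITP risk difference with 95% CI | Placebo-controlled, but counts adverse events |

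The last row depends on an elevation being reported as an adverse event. Protocol 8.2.1 leaves that to the Investigator's view of clinical significance. Appendix 6 requires all PDILI events to be reported as AEs, but the row of Table 10-3 for participants without symptoms and with bilirubin <2xULN begins at 5xULN. An isolated, asymptomatic ALT or AST between 3x and 5xULN therefore reaches the hepatic-event analysis only through Investigator judgement.

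**2. Baseline.** The general markedly abnormal table excludes Baseline values explicitly; the liver paragraph does not. Exclusion criterion 19 rules out ALP >=3xULN at Screening, so a participant enrolled with ALP at 2xULN would meet the >1.5xULN criterion before any IMP. Among the listed criteria, this affects the ALP row.

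**3. Person-time of a placebo-randomised completer.** Inputs: ITP of 112 days (SAP 4.5.1.1); last dosing visit at Week 28 (SAP 6.11); on-treatment window to last dose + 119 days (SAP 4.5.3.1).

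- End of window: 28 x 7 + 119 = 315 days.
- On placebo: 112 / 315 = 35.6%.
- After the switch: 315 - 112 = 203 days; 203 / 315 = 64.4%.
- Scheduled post-Baseline biochemistry (Protocol Table 1-1, assuming the columns were read correctly): Weeks 4, 16, 20, 24, 32 and SFU. Four of the six follow the switch.

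**4. Illustration of dilution.** The plan gives no liver event rates, so the 16-week risks of ALT/AST >3xULN below are assumptions: p0 on placebo, p1 on bimekizumab. The hazard is taken as constant and columns as randomised sequence.

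- Placebo sequence: 1 - (1 - p0)(1 - p1)^(203/112).
- Bimekizumab sequence: 1 - (1 - p1)^(315/112).

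| Assumed ITP risks | ITP ratio | Whole-study risks | Whole-study ratio |
|---|---|---|---|
| 1% vs 3% | 3.0 | 6.3% vs 8.2% | 1.30 |
| 1% vs 5% | 5.0 | 9.8% vs 13.4% | 1.37 |
| 2% vs 5% | 2.5 | 10.7% vs 13.4% | 1.26 |
| 1% vs 10% | 10.0 | 18.2% vs 25.6% | 1.41 |

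The loss is mainly on the ratio scale. In the first row the absolute difference moves only from 2.0 to 1.9 percentage points.

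**5. What an ITP table could show.** Allocation: 120 x 3/4 = 90 and 120 x 1/4 = 30. At a 1% placebo risk, 30 x 0.01 = 0.3 events are expected. With 0/30 observed, the exact two-sided 95% upper limit is 1 - 0.025^(1/30) = 11.6%. Approximate power over the four scenarios runs from 4% to 29%.

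**The case against.** The strongest reply is that the split is already there. The liver paragraph describes an extension of the markedly abnormal table. That table is produced for the ITP and for the combined period, excludes Baseline values, and has a rule attributing results to periods by sampling date. The 4.1.4 default for ITP safety data is Placebo versus BKZ Q4W on the SS. On this reading, one table means one layout holding all the liver cut-offs, and the ALP example disappears. This reading is possible, but it sits badly with the explicit words for a single table covering the whole study, next to three summaries that each ask for two. Two programmers could reasonably produce different outputs.

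A reader might also infer that liver elevations below Grade 3 have no placebo-controlled comparison at all. The documents do not support that. The ITP hepatic-event risk difference covers broad and narrow terms without a severity or causality limit, and the by-visit laboratory values through Week 16 are placebo-controlled. The gap is confined to threshold counts of laboratory values.

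A reader might take the fall in ratio from 3.0 to 1.3 as a property of the plan. It is not. It needs assumed rates, one hazard carried unchanged through Q4W, Q8W and follow-up, and sequence columns that the SAP does not specify for this table. With AMS columns there would be no such ratio, only a missing placebo column.

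Nor do the documents show the same defect in the pDILI and Hy's Law tables. Their period is simply not stated. The objection that an ITP table would have low power stands.

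**Conclusion.** The point holds in a limited form: as written, the SAP contains no ITP table that counts participants with laboratory liver elevations below Grade 3 against placebo. The affected range is ALT/AST above 3x and up to 5xULN, bilirubin above 1.5x and up to 3xULN, and ALP above 1.5x and up to 5xULN. This rests on a literal reading of the single whole-study table and on SAP 6.13 having no liver rows. The 64% share of post-switch time follows from the documents for a completer followed through the 119-day window; the dilution ratios are illustrative only.

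No confirmatory result depends on this table, and the data are already collected. It is a cheap improvement to the reporting of a prespecified safety topic.

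**What to change.** In SAP 4.5.3.1, replace the single whole-study instruction with two tables using the same cut-offs, post-Baseline values only, and the section's existing rule that attributes results by sampling date and time at risk:

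1. ITP, SS, Placebo versus BKZ 320mg Q4W.
2. Combined period, AMS, BKZ 320mg Q4W, Q8W and Total. As 4.1.4 already provides, participants randomised to placebo contribute only data after the switch.

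The cost is a few words in the SAP and one extra descriptive output from the same program. It needs no new data and changes no clinical rule. Stating the period of the pDILI and Hy's Law tables in the same edit would be useful housekeeping, but this point does not depend on it.
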